## 5. SUBJECT ENROLLMENT

Before subjects begin participation in any study-specific activities/procedures, Amgen requires a copy of the site's written institutional review board/independent ethics

committee (IRB/IEC) approval of the protocol, informed consent form, and all other subject information and/or recruitment material, if applicable (see [Section 11.2](#)).

Subject must personally sign and date the IRB/IEC and Amgen approved informed consent form before the commencement of study-specific procedures. Upon completion of the screening period the subject is evaluated by the investigator and providing the subject continues to meet the inclusion/exclusion criteria, the subject is subsequently eligible to be enrolled in the study and assigned to a treatment regimen (dose cohort).

A subject is considered enrolled when the investigator decides that the subject has met all eligibility criteria. The investigator is to document this decision and date, in the subject's medical record and in/on the enrollment case report form (CRF).

Each subject who enters into the screening period for the study receives a unique subject identification number before any study-related activities/procedures are performed. The subject identification number will be assigned manually. This number will be used to identify the subject throughout the clinical study and must be used on all study documentation related to that subject. A subject may be rescreened up to 3 additional times during the study at the discretion of the investigator.

The subject identification number must remain constant throughout the entire clinical study; it must not be changed after initial assignment, including if a subject is rescreened.

There will be a 96-hour interval between the start of treatment of each subject entered on study. See [Section 6.2.1.4.2](#) for interruption of blinatumomab treatment/dose modification due to adverse events.

## **5.1 Treatment Assignment**

This is an open-label study. Subjects, investigators and the study team will all be aware of the assigned dose of blinatumomab.

An Amgen representative will notify the sites when a cohort is open to screen new subjects. Once a site has confirmed eligibility of a screened subject, the site will be informed in writing about the applicable dose for the dose cohort the subject will be assigned to.

The treatment assignment date is to be documented in the subject's medical record and on the enrollment CRF.

## 6. TREATMENT PROCEDURES

### 6.1 Classification of Product

The Amgen Investigational Product used in this study is blinatumomab.

The Investigational Product Instruction Manual (IPIM), a document external to this protocol, contains detailed information regarding the storage, preparation, destruction, and administration of blinatumomab.

Other protocol-mandated medication (eg, dexamethasone used for pre-dose treatment or for treatment of adverse events) are commercially available and are not provided or reimbursed by Amgen (except if required by local regulation). The investigator will be responsible for obtaining supplies of these protocol-specified therapies.

### 6.2 Investigational Product

#### 6.2.1 Amgen Investigational Product Blinatumomab

Blinatumomab will be manufactured and packaged by Amgen and distributed using Amgen clinical study drug distribution procedures.

Blinatumomab will be supplied as a 4 mL single-use glass injection vials as a sterile, preservative-free, white to off-white, lyophilized powder for intravenous (IV)/SC administration, respectively, after reconstitution with sterile water for injection.

Blinatumomab for cIV administration is formulated with citric acid monohydrate, trehalose dihydrate, lysine hydrochloride, and polysorbate 80, pH 7.0. Each vial contains 38.5 µg blinatumomab.

Blinatumomab for SC administration is formulated with 10 mM potassium phosphate, 4% (w/v) mannitol, 2% (w/v) sucrose, 1% (w/v) sulfobutylether beta-cyclodextrin, 0.01% (w/v) polysorbate 80, pH 7.0. Each vial contains 1.0 mg blinatumomab.

#### 6.2.1.1 Dosage, Administration, and Schedule

Blinatumomab will be administered as cIV via a central line (not peripheral) or SC. Exceptions for technical difficulties with the central line may be made after discussing with the Amgen medical monitor.

For SC administration, there is an allowed time window of  $\pm 1$  hour for the q12h, q24h, **q48h, q72h, q96h, and q7d** dosing.

The dose, start and stop date/time, and lot number of the protocol-specified therapy are to be recorded on each subject's CRF.

Approved

The dosing schedule is described by study schemas in [Figure 1](#) and [Figure 2](#) at the end of the protocol synopsis section.

#### 6.2.1.1.1 Cycle 1/Period 1

Cycle 1/Period 1 will consist of blinatumomab administered as a cIV infusion for 21 days (**weeks 1 to 3**) of treatment and in addition, any number of days required to bridge cIV dosing so that SC dosing begins on a Monday (unless the study site can administer SC injections on the weekend), followed by a **12-hour treatment free period**.

**Then subjects will receive SC dosing in week 4 followed by a treatment free period of 2 to not more than 3 days, and then subjects** return to cIV administration for 2 weeks (**weeks 5 to 6**) to complete a total of **6 weeks** of treatment.

The initial dose of blinatumomab will be 9 µg/day cIV for the first 7 days (to mitigate for potential CRS and neurologic events associated with introduction to blinatumomab) and then the dose will be escalated (dose-step) to 28 µg/day cIV starting on day 8 through day 14 (week 2), and to 112 µg/day cIV starting on day 15 **through 21** (week 3).

If there are any interruptions in treatment that lead to the start day of SC dosing to be on a weekend day, then cIV dosing will be continued at the maximum dose and stopped 12 hours before starting the SC injections, which can commence on a Monday if not logistically feasible to administer SC injections on a weekend day.

After completion of the initial cIV blinatumomab run-in period, **there is a treatment free period of 12 hours, then** SC blinatumomab will be administered **daily** for 5 days (week 4) **for dose cohort 1, 2, and 3. The SC dose and frequency will be chosen by the DLRT for further cohorts (see [Figure 1](#)).** After completing SC dosing there is **at least 2 days to not more than 3 days of no investigational product, followed by a return to investigational product at 112 µg/day cIV administration for 2 weeks (weeks 5 and 6) to complete a total of 6 weeks of therapy.** (Note: A total of 9 SC doses will be given for the q12h dosing, so intensive PK samples can be obtained on day shift to reduce errors).

#### 6.2.1.1.2 Cycle 1/Period 2

Subjects will receive the estimated SC equivalent doses of the 2 lower cIV doses as **given** in the cIV blinatumomab run-in period sequentially: **2 doses of the equivalent SC dose to 9 µg/day of cIV during week 1, 3 doses of the equivalent SC dose to 28 µg/day cIV starting in week 1 and continuing into week 2, and then the SC MTD (or the maximum tested dose if MTD is not reached) and SC dosing interval as**

determined in Cycle 1/Period 1 starting in week 2 (day 12) and continuing to complete a total of 6 weeks of blinatumomab (Figure 2).

**6.2.1.1.2.1 Special Case of SC Dosing Interruptions and Weekend Dose Holds for Cycle 1/Period 1.**

For dose cohorts 1, 2, and 3 the SC administration of blinatumomab will occur over 5 days in Cycle 1/Period 1. If administration at a study site is feasible on weekends, then SC administration may commence any day of the week. If weekend administration of blinatumomab at a study site is not feasible, then SC administration should commence on a Monday so that the fifth day of dosing can be given on a Friday.

In instances where there is a dose interruption during the SC administration, and the site does not have the ability to restart dosing on a weekend day, the subject should have the dose held over the weekend and resume dosing the next available weekday.

Premedication dexamethasone will be given as per protocol after an interruption (Table 1) of cIV and SC dosing.

**6.2.1.1.3 Optional Cycle 2**

**Optional Cycle 2 for Period 1:** A subject may receive a second cycle of blinatumomab if, in the investigator's opinion, the subject may derive benefit from the treatment. The optional cycle 2 of blinatumomab will be dosed at 9 µg/day cIV for 7 days for days 1 through day 7, next the dose will be escalated (dose-step) to 28 µg/day cIV for 7 days starting on day 8 through day 14, and then advanced to 112 µg/day cIV for 28 days starting on day 15 through day 42. A treatment free interval of 14 days will be observed after the completion of the first cycle of blinatumomab before starting the second cycle.

**Optional Cycle 2 for Period 2:** A subject may receive a second cycle of blinatumomab administered SC if the subject had clinical benefit on scans from treatment given SC in Cycle 1/Period 2 (Section 6.2.1.1.2).

If no clinical benefit on scans after Cycle 1/Period 2, then optional Cycle 2 is administered as a cIV infusion. If cIV is used, blinatumomab will be dosed at 9 µg/day cIV for 7 days for days 1 through day 7, next the dose will be escalated (dose-step) to 28 µg/day cIV for 7 days starting on day 8 through day 14, and then advanced to 112 µg/day cIV for 28 days starting on day 15 through day 42. A treatment free interval of 14 days will be observed after the completion of the first cycle of blinatumomab before starting the second cycle.

Approved

#### **6.2.1.1.4 Blinatumomab Inpatient Dosing**

It is mandated in this study that subjects are hospitalized at least during the first 72 hours at the start of cIV infusion (Cycle 1/Period 1, Optional Cycle 2/Period 1, and **Optional Cycle 2/Period 2 if administered as a cIV infusion**) as well as after any additional dose-step. Hospitalization is also required during the first 48 hours after the return to cIV infusion after the SC dosing in Cycle 1/Period 1. Subjects will remain hospitalized during the entire SC administration dosing in Cycle 1/Period 1.

In Cycle 1/Period 2, **subjects are hospitalized: For subjects 1-5: day 1 until completion of the second MTD dose PK being finished. Sites where outpatient PK cannot be obtained, for the third MTD SC dose, the subject needs to be hospitalized until completion of the third MTD dose PK. Subjects 6-15: are hospitalized on days 1-8 (discharge 8 hours after day 8, 28 µg/day equivalent SC dose is administered) and readmitted to the hospital on day 12 (prior to first MTD SC dose) until 8 hours after the second MTD SC dose is administered. Sites where outpatient PK cannot be obtained, for third 28 ug/day equivalent SC dose and third MTD SC dose, the subject needs to be hospitalized until completion of the third MTD dose PK.**

In **Optional Cycle 2/Period 2, if given SC subjects are hospitalized on days 1-8 (discharge 8 hours after day 8, 28 µg/day equivalent SC dose is administered) and readmitted to the hospital on day 12 (prior to first MTD SC dose) until 8 hours after the second MTD SC dose is administered.** The infusion bags will be changed (**if IP is administered as a cIV infusion**) and SC injections administered by trained site nursing personnel. Close monitoring during the first 72 hours of treatment at each dose will be required because of the potential for adverse events.

#### **6.2.1.1.5 Blinatumomab Outpatient Dosing and Home Health Care Administration for cIV and SC Dosing**

If a subject is deemed stable by the investigator, the subject may continue blinatumomab (cIV [in all periods] or SC administration [in Cycle 1/Period 2 only]) as an outpatient.

In the outpatient setting, the subject will return to the study site or the subject will be visited by a well-trained home health care service provider at specific intervals to change the infusion bag or for administration of the SC injection, as applicable. The subject and the home health care provider will receive written instructions for storage of the IV bags and/or blinatumomab for SC administration as applicable.

The home health care provider will be trained on study-specific requirements, recording of source documentation, and completion of the study delegation log (authorized by the investigator) must be completed before any study-related tasks are started. A comprehensive list of all home care services, including but not limited to the storage, handling, and administration of blinatumomab as well as mandatory procedural and data collection requirements will be provided in a home health care manual. Following each visit, this information will be documented on the Ambulant/Home Care Services visit worksheet and forwarded to the investigator. Any unexpected or unusual events as well as any deviations will be communicated promptly to the investigator. In addition, the subject will visit the study site for assessments according to [Table 3](#), [Table 4](#), [Table 5](#), [Table 6](#), and [Table 7](#).

In the event of drug interruptions refer to [Section 6.2.1.4.1](#).

In case of an adverse event occurring in the outpatient setting, the subject or the home health care service provider should contact the investigator immediately at the study center for further instruction on management and the investigator will assess the adverse event.

#### **6.2.1.1.6 Overdose**

The daily blinatumomab cIV dose may be up to 10% lower or higher in order to account for possible pump inaccuracies. **A dose of up to 10% higher than the intended dose may not require specific intervention. In case of overdose or medication error, the infusion should be immediately stopped. Consultation with the Amgen medical monitor is strongly recommended for prompt reporting of clinically apparent or laboratory adverse events possibly related to overdose. Routine supportive and symptomatic care according to standard medical practice is recommended. Once the subject is stabilized and no clinically relevant safety findings due to blinatumomab are observed, resumption of blinatumomab at a correct dose can be considered after consultation with the Amgen medical monitor.**

**If the overdose results in an adverse event, the subject should be followed carefully until all signs of toxicity are resolved and the adverse event(s) should be recorded/reported.** If the overdose results in clinically apparent or symptomatic adverse events or additional adverse events, the subject should be followed carefully until all signs of toxicity are resolved and the adverse event/s should be recorded/reported per [Section 9](#).

In the SC route of administration, any dose above the planned dose will be considered an overdose. In the event of any overdose, subjects should be observed and clinically evaluated for at least **the dosing interval the subject was assigned without receiving any further doses of SC injection (eg, if subject assigned to q24h, to be evaluated for 24 hours)**. After that period of time, if the subject has not developed any adverse events or serious adverse events, dosing may be resumed after consultation with the Amgen Medical Monitor. If the subject has developed any adverse events or serious adverse events see dose interruption rules as outlined in [Section 6.2.1.4](#). Any dose above the planned dose of blinatumomab for SC dose will be considered clinically important and classified as a serious adverse event under the criterion of “other medically important serious event” per [Section 9.1.3](#).

### **6.2.1.2 Dose-cohort Study Escalation and Stopping Rules**

#### **6.2.1.2.1 Dose Level Review Team**

The DLRT meeting will be held to review data, monitor safety, and make decisions on dose escalation/change, or changes in pre-medication. The DLRT will be composed of the investigators or designees, and the following Amgen representatives: medical monitor, global safety officer or designee, clinical trial manager, biostatistician, PK scientist (optional), site investigator or designee, and other functional area representatives as appropriate. A quorum as defined below must be in attendance for the DLRT. The quorum is defined as > 50% of the participating investigators (**defined as the number of investigators that had subjects enrolled on the cohort for that DLRT meeting**) or their qualified designee (ie, sub-investigator or research nurse or study coordinator possessing written documentation [eg, e-mail] of the investigator’s vote), as well as > 50% of Amgen representatives listed above. The medical monitor or designee must attend for the quorum to be reached. The DLRT will be rescheduled if a quorum is not reached.

The following members are responsible for DLRT decisions: investigators, Amgen medical monitor, and global safety officer or designee.

The following decisions may be made by the DLRT:

- dose escalation/de-escalation decisions
- **changes in dosing frequency**
- expansion of a cohort
- continuation, delay or termination of dosing

All available study data, including demographics, investigational product administration, medical history, concomitant medications, adverse events, vital signs, laboratory data, and PK/PD information will be reviewed. In addition to DLTs, all  $\geq$  grade 3 toxicities not meeting DLT criteria will be reviewed and may be considered in DLRT decisions.

Source data and queries do not need to be resolved before the DLRT. Continuous toxicity monitoring for early termination of the trial in Cycle 1/Period 2 will be performed. All adverse events that occur during the DLT evaluation period will be reviewed and may be considered in DLRT decisions.

#### 6.2.1.2.2 Dose Limiting Toxicity Rules

##### Cycle 1/Period 1

The DLT evaluation period includes the entire **week 4 (7 days) which is the week that blinatumomab is administered** SC during Cycle 1/Period 1 of the study. To be evaluable for a DLT, subjects must have experienced a DLT within the DLT evaluation period. In addition, if the investigator and/or sponsor removes the subject from the study due to a treatment-related toxicity during the DLT evaluation period, regardless of the grade of toxicity, this will be considered a DLT. If a subject does not experience a DLT during the DLT evaluation period and does not receive **all doses (q48h, q72h, q96h, or q7d dosing)**, at least 4 of the 5 doses (q24h dosing), or at least 8 of 9 doses (q12h dosing) of **SC** blinatumomab during Cycle 1/Period 1 of the study, the subject will not be considered DLT-evaluable and will be replaced as described in [Section 3.4.1](#).

If  $\leq 1$  of the 6 evaluable subjects in a dose SC cohort experience a DLT during the SC administration, then the dose will be determined to be tolerable and the next dose-cohort level will be initiated in a new dose-cohort of subjects after review by the DLRT.

If  $\geq 2$  subjects of the 6 evaluable subjects in a SC dose cohort experience a DLT during SC administration then dosing will stop for individual subjects who experience a DLT, a DLRT meeting will be conducted, and further steps will be determined.

Additionally, the DLRT will meet:

- once dose-cohort 1 has completed subcutaneous dosing
- once dose-cohorts 2 and 3 have completed subcutaneous dosing
- once any additional cohorts complete dosing if additional dose-cohorts are tested to determine the MTD in Cycle 1/Period 1

## Cycle 1/Period 2

For subjects who receive optional Cycle 2 after Cycle 1/Period 2 (SC dosing period), the DLT evaluation period includes the entire duration of SC administration **in Cycle 1** and 16 days following the last SC dose (56 days in total) or until the start of optional Cycle 2, whichever is longer, up to 30 days after the last SC dose **of Cycle 1**.

For subjects who do not receive optional Cycle 2, the DLT evaluation period includes the entire duration of SC administration and 30 days following the last SC dose (70 days in total).

Continuous monitoring for early termination of the trial will be performed (refer to [Section 10.2](#)).

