### 6.2.1.2.3 Dose Limiting Toxicities

All toxicities will be graded using the Common Terminology Criteria for Adverse Events (CTCAE) version 4.0 (see [Appendix D](#)). The occurrence of any of the following toxicities during the DLT evaluation period will be considered a DLT, if judged by the investigator to be related to the administration of blinatumomab:

- Any treatment-related death
- Any treatment-related toxicity, regardless of grade, that leads to a subject's removal from the study by the investigator and/or sponsor
- Persistent CTCAE grade  $\geq 2$  non-hematologic adverse events related to blinatumomab that are deemed intolerable by the subject or the treating physician and that do not respond to appropriate medical management within 5 days and lead to treatment discontinuation will be considered DLTs
- Recurrent grade 2 seizures ie, brief generalized seizures
- All grade 3 and 4 adverse events and laboratory abnormalities, which occur during the SC administration portion of the treatment period and which, in the opinion of the investigator, are at least possibly related to the investigational drug, are considered as DLT with exceptions noted below:
  - Laboratory parameters of grade  $\geq 3$  that responds to intervention/treatment interruption and resolves to grade  $\leq 1$  within 7 days
  - **Grade 3 and 4 lymphopenia**
  - Grade 3 fever or infection
  - Grade  $\leq 3$  events of CRS or tumor lysis syndrome that responds to intervention/treatment interruption and resolves to grade  $\leq 1$  within 7 days
  - **Grade 3 neurologic events that respond to intervention/treatment interruption and resolves to grade  $\leq 1$  within 7 days**

Approved

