b If a subject has a dose interruption during the SC administration period and that dose needed to be provided on a weekend, then the dose will be held and dosing will resume on the next business day if the site is unable to administer SC dosing on weekends due to local feasibility challenges. In that case, despite any extra days added due to treatment interruption in the cIV portion, day 22 still refers to the first day of SC administration.

c During SC dosing, at q12h, q24h, q48h, and q96h, PK samples are collected for the first dose on day 22 (pre-dose, as well as 1 hour ± 15 minutes, 2 hours ± 15 minutes, 4 hours ± 30 minutes, 6 hours ± 30 minutes, 8 ± 1 hours, and 12 ± 1 hour (before the next q12h dose if applicable) and for the last dose on day 26 (pre-dose, as well as post-dose at 1 hour ± 15 minutes, 2 hours ± 15 minutes, 4 hours ± 30 minutes, 6 hours ± 30 minutes, 8 ± 1 hours, 12 ± 1 hours, as well as 24 ± 2 hours (day 27), and 48 ± 2 hours (day 28).

d In the return to cIV dosing following the 5 treatment days of SC administration, PK samples are collected at any time during the day on the second day (day 30) after resuming 112 µg/day cIV dose (day 29). Refer [Section 7.3.15.1](#) for detail, sampling window and handling if dose interruption occurred.

e For the SC q72h dosing regimen, PK samples are collected for the first dose on day 22 (pre-dose, as well as 1 hour ± 15 minutes, 2 hours ± 15 minutes, 4 hours ± 30 minutes, 6 hours ± 30 minutes, 8 ± 1 hours, and 12 ± 1 hour and for the last dose on day 25 (pre-dose, as well as post-dose at 1 hour ± 15 minutes, 2 hours ± 15 minutes, 4 hours ± 30 minutes, 6 hours ± 30 minutes, 8 ± 1 hours, 12 ± 1 hours, as well as 24 ± 2 hours (day 26), 48 ± 2 hours (day 27), and 72 ± 2 hours (day 28).

f For the SC q7d dosing regimen, PK samples are collected for the dose on day 22 (pre-dose, as well as 1 hour ± 15 minutes, 2 hours ± 15 minutes, 4 hours ± 30 minutes, 6 hours ± 30 minutes, 8 ± 1 hours, and 12 ± 1 hour as well as 24 ± 2 hours (day 23), 48 ± 2 hours (day 24), 72 ± 2 hours (day 25) and 96 ± 2 hours (day 26).

Approved

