8.1.1.2 Dose Limiting Toxicity Rules

Cycle 1/Period 1

The DLT evaluation period includes the entire week 4 (7 days) which is the week that blinatumomab is administered SC during Cycle 1/Period 1 of the study. To be evaluable subjects need to fulfill the criteria described in [section 6](#).

If ≤ 1 of the 6 evaluable subjects in a dose SC cohort experience a DLT during the SC administration, then the dose will be determined to be tolerable and the next dose-cohort level will be initiated in a new dose-cohort of subjects after review by the DLRT.

If ≥ 2 subjects of the 6 evaluable subjects in a SC dose cohort experience a DLT during SC administration then dosing will stop for individual subjects who experience a DLT, a DLRT meeting will be conducted, and further steps will be determined.

Additionally, the DLRT will meet:

- once dose-cohort 1 has completed subcutaneous dosing
- once dose-cohorts 2 and 3 have completed subcutaneous dosing
- once any additional cohorts complete dosing if additional dose-cohorts are tested to determine the MTD in Cycle 1/Period 1

Cycle 1/Period 2

For subjects who receive optional Cycle 2 (cIV dosing period) after Cycle 1/Period 2 (SC dosing period), the DLT evaluation period includes the entire duration of SC administration in Cycle 1 and 16 days following the last SC dose (56 days in total) or until the start of optional Cycle 2, whichever is longer, up to 30 days after the last SC dose of Cycle 1. For subjects who do not receive optional Cycle 2, the DLT evaluation period includes the entire duration of SC administration and 30 days following the last SC dose (70 days in total). Continuous monitoring for early termination of the trial will be performed by DLRT (refer to [Section 3.1.3](#) and [Section 8.1.1](#)).

9. Data Screening and Acceptance

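### Period 1 defines a 7-day DLT window but counts DLTs, and calls the dose review, by the SC dosing days; the two need one time base

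*Protocol*

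**What the plan says.** **The window.** SAP 8.1.1.2 states: "The DLT evaluation period includes the entire week 4 (7 days) which is the week that blinatumomab is administered SC". Protocol 6.2.1.2.2 agrees: "week 4 (7 days) which is the week that blinatumomab is administered". Protocol Tables 3 and 4 number this week as days 22 to 28.

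**The meeting trigger.** In the same two sections the DLRT meets "once dose-cohort 1 has completed subcutaneous dosing", "once dose-cohorts 2 and 3 have completed subcutaneous dosing", and "once any additional cohorts complete dosing if additional dose-cohorts are tested".

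**The counting rule.** In Protocol 6.2.1.2.2 the tolerable arm requires no more than one DLT among six subjects and gives the time base as follows: "evaluable subjects in a dose SC cohort experience a DLT during the SC administration, then the dose will be determined to be tolerable". The arm for 2 or more DLTs uses the same time base, and SAP 8.1.1.2 repeats both arms. The Synopsis, Protocol 3.1.1 and SAP 3.1.1 differ: their arm for at most 1 of 6 refers to the DLT evaluation period, while their arm for 2 or more again refers only to SC administration.

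**The DLT definition.** Protocol 6.2.1.2.3 opens by counting the listed toxicities over the DLT evaluation period. Its main bullet then restricts grade 3 and 4 events to the SC administration portion of treatment. Several events are exempt if they resolve within 7 days, among them "Grade 3 neurologic events that respond to intervention/treatment interruption and resolves to grade" 1 or lower.

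**Evaluability.** A subject without a DLT becomes evaluable by the number of SC doses received. No minimum follow-up to day 28 is stated.

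**The concern.** The documents use two time bases for one decision. One is the full week. The other is the SC dosing days, which end on day 26 or earlier, followed by drug-free days that still lie inside the window. A DLT on one of those days falls within the stated evaluation period. It may nevertheless be left out of a count made during SC administration, or not yet have happened when the DLRT meets.

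The two arms of the rule can also fail to meet. Take a cohort with one DLT on a dosing day and a second on day 27. Under the literal wording of Protocol 3.1.1 it has two DLTs over the evaluation period, so the tolerable arm is not met. It has one DLT during SC administration, so the arm for 2 or more is not met either.

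The count of 1/6 or 2/6 decides whether a dose is tolerable, informs the next dose and interval, and fixes the MTD taken to Period 2. A single event on days 27 to 28 can change the decision. SC dosing is first-in-human here and safety is the primary endpoint, so the count should have one unambiguous definition.

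**Working it through.** **1. The plan's own figures.** Protocol 10.2 gives the chance of at most 1 DLT in 6 as 89% at a true rate of 10% and 42% at 30%. With P = (1−p)^6 + 6p(1−p)^5:

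- p = 0.10: 0.5314 + 0.3543 = 0.8857
- p = 0.30: 0.1176 + 0.3025 = 0.4202

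Both reproduce. They assume that all six subjects are observed for the whole window.

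**2. Days left at the trigger.** The last SC dose day comes from the footnotes to Protocol Table 4. For q7d the only dose is the first day of the week: "For the SC q7d dosing regimen, PK samples are collected for the dose on day 22". The gap is 28 minus the last dose day.

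| Interval | Last SC dose | Gap to day 28 | Last scheduled SC PK sample | Gap after that sample |
|---|---|---|---|---|
| q12h, q24h, q48h, q96h | day 26 | 2 days | day 28 | 0 days |
| q72h | day 25 | 3 days | day 28 | 0 days |
| q7d | day 22 | 6 days | day 26 | 2 days |

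Cohorts 1 to 3 are q12h or q24h, so their gap is 2 days. As extracted, Table 4 also marks dosing on day 27 for q12h and q24h. That conflicts with its own footnote and the 5-day text and may be an extraction fault; if real, that gap is 1 day.

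**3. Effect of deciding at the trigger.** The documents give no DLT timing, so I assume a constant hazard over the 7 days and that only the last subject's window is open. With gap g, that subject's chance of an observed DLT is p′ = 1 − (1−p)^((7−g)/7). Let A be the chance of at most 1 DLT in the other five subjects and B the chance of exactly 1. Then P(at most 1 seen) = A − p′B.

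- p = 0.10: A = 0.9185, B = 0.3281
- p = 0.30: A = 0.5282, B = 0.3602

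| Gap | p′ at 10% | P(at most 1) | Rise | p′ at 30% | P(at most 1) | Rise |
|---|---|---|---|---|---|---|
| 2 days | 0.0725 | 89.5% | 0.9 points | 0.2249 | 44.7% | 2.7 points |
| 3 days | 0.0584 | 89.9% | 1.4 points | 0.1844 | 46.2% | 4.2 points |
| 6 days (q7d) | 0.0149 | 91.4% | 2.8 points | 0.0497 | 51.0% | 9.0 points |

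Example, 2 days at 30%: 0.5282 − 0.2249 × 0.3602 = 0.4472, against 0.4202.

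**4. Sensitivity to a second open window.** With two subjects each 2 days short, the rises are 1.8 and 5.5 points. For q7d with SC starts exactly 96 hours apart (6 and 2 days left), P(at most 1) is 92.2% and 54.1%, rises of 3.6 and 12.0 points. The 96-hour spacing is an assumption for SC starts: Protocol 5 spaces the start of treatment, and bridging to a Monday can move SC starts closer together or further apart.

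**5. Pending events.** An event that starts on day 28 can still qualify for the 7-day exception until day 28 + 7 = day 35. No section says how the DLRT counts it in the meantime.

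**The case against.** The opposing case is strong and narrows the point.

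- **The trigger is a milestone.** A reader might infer that the plan permits escalation before the window closes. It does not say so. Meeting once dosing is complete sets an earliest time, not a duty to decide that day. Protocol 3.1.1 ties tolerability to the DLT evaluation period, and 6.2.1.2.1 has the DLRT review the adverse events of that period. This stands, and is why the point is one of inconsistency.
- **SC administration may mean the whole week.** Table 4 puts days 22 to 28 under a subcutaneous administration heading. But Table 3 footnote e separates 5 days of SC administration from 2 drug-free days. The documents use the phrase both ways, so they do not establish that events in the drug-free days are excluded for all six subjects.
- **PK will hold the meeting back.** SAP Appendix F calls PK data essential to the decision. Waiting for the last sample removes the gap except for q7d. That is likely in practice, but no section requires it.
- **The run-in gives time to react.** New Period 1 subjects have 21 days of cIV before SC dosing, and Protocol 10.3.1 keeps DLTs under continual review. This stands for Period 1. Period 2 has no cIV run-in and reaches the MTD dose on day 12.

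Three further inferences fail:

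- **Events still open do not lower the count.** A related grade 3 event that has not resolved has not met the exception. On the wording it counts as a DLT unless it resolves in time.
- **The gap is not longer for every long interval.** q48h and q96h have the same 2 days as q12h.
- **Cohorts 2 and 3 need not share one meeting.** The meeting list is introduced as additional to the review required before each next cohort.

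**Conclusion.** The inconsistency is real and should be corrected, at lower severity than a design fault. The stated window is 7 days; the trigger, the counting phrase in Protocol 6.2.1.2.2 and SAP 8.1.1.2, the arm for 2 or more DLTs in every section, and one bullet of the DLT definition all point to a shorter time base.

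For cohorts 1 to 3 the effect is small: 0.9 points at a 10% true DLT rate and 2.7 points at 30%, or nothing if the meeting waits for the day 28 PK sample. It is material only for a q7d cohort: 2.8 and 9.0 points at the trigger. If the meeting waits for that regimen's day 26 sample, the gap is 2 days and the rise 0.9 and 2.7 points.

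These figures assume constant hazard, one open window and a decision on the last dosing day. They size only what the DLRT has not yet seen. They do not size a reading that excludes drug-free days for all six subjects, which the window definition speaks against.

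**What to change.** Reconcile the Synopsis, Protocol 3.1.1, 6.2.1.2.2 and 6.2.1.2.3, and SAP 3.1.1 and 8.1.1.2, as follows:

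- Count DLTs over the full DLT evaluation period in both arms of the 1/6 versus 2/6 rule, and give the grade 3 and 4 bullet the same time base.
- State that the DLRT makes its tolerability, escalation and MTD decision only after the last evaluable subject has completed the DLT evaluation period or had a DLT. The completion-of-dosing milestone can stay for scheduling the meeting.
- State how an event still pending under a 7-day resolution exception is counted at the meeting.

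The cost is wording in both documents, plus usually 0 to 2 days per meeting. The most it could add is 3 days for q72h and 6 days for q7d. Sample size and analysis do not change.
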